Including determination of working length, degree of foraminal enlargement, number of visits, analgesics consumption, gender ⁽²⁻⁵⁾, technique of filing and instrumentation system, kinematics, trauma of periapical tissue or bacterial extrusion and root canal sealer. specifically, extrusion of root canal sealer can disrupt periodontal tissues and cause inflammatory reactions. The intensity of this reaction depends on the composition of the sealer.

Different types of sealers can be used during obturation of root canals like zinc oxide and eugenol sealers, resin sealers or bio ceramic sealers. Resin sealers maybe epoxy, or methacrylate based, they are radiopaque, have low solubility and are biocompatible and have good flow while bio ceramic sealers contain alumina, zirconia particles, bioactive glass, calcium silicates, hydroxyapatite, and resorbable calcium phosphates ⁽⁶⁾. These ingredients allow the sealers to resist bacterial leakage, rendering it biocompatible, simulating dynamic intratubular biomineralization. Bioceramic sealers release bioactive substances and enhance endodontic treatment outcomes by facilitating the differentiation of odontoblasts. However, resin sealers show higher bonding strength and radiopacity compared to bioceramic sealers.

Bioceramic sealers were introduced into the market as to cause less post operative pain after obturation compared to other sealers that is why studies were conducted to validate this fact with evidence.

The null hypothesis is that there is no difference in post operative pain between resin and bio ceramic sealers after endodontic treatment.

Review of Literature

Postoperative pain is defined as pain of any degree after initiation of root canal treatment either intra-appointment or post-obturation and is considered an undesirable occurrence for both patient and clinician.⁽⁷⁾

After cleaning and shaping of the canals Obturation can be performed using different types of sealers.

- Resin sealers are classified to epoxy resin based or methacrylate-based resin sealers. Epoxy resin-based sealers are commonly used due to their low solubility, micro-retention to dentin of root canal and their good apical seal. Currently modifications of the original formula are used widely⁽⁸⁾. Epoxy resin-based sealers are characterized by the reactive epoxide ring and are polymerized by these rings.
- Bio ceramic sealers are sealers that contain **calcium silicate and/or calcium phosphate** as their main compositions. Bioactive materials, such as glass and calcium phosphate, interact with the surrounding tissue to encourage the growth of more durable tissues⁽⁹⁾, it can penetrate the dentinal tubules and interact with dentine moisture to create bonds between the dentin and core filling materials, an optimum dimensional stability, and the least amount of shrinkage.
(10)

Pain is evaluated using visual analogue scale (VAS)⁽¹¹⁾

- It is a pain rating scale. Scores are based on measures that are self-reported of symptoms that are recorded through a single handwritten mark placed at one point along the length of a 10-cm line representing a continuum between the two ends of the scale— on the left end of the scale (0 cm) means “no pain “and the on the right end of the scale (10 cm) “worst pain “

Pak and White ⁽¹²⁾conducted a systematic review to assess the prevalence and severity of pretreatment, treatment, and post-treatment pain in patients receiving root canal treatment. They reviewed 72 studies for meta-analysis and concluded that pretreatment endodontic pain of high intensity dropped moderately within 1 day reaching minimal levels after 7 days & post-treatment pain prevalence was moderate or low stating that most included articles reported 7-day pain relief as the severity starts to drop from the first day till less than 10% after 7 days.

Ali et al., ⁽¹³⁾investigated the prevalence of post-operative pain after single visit endodontic treatment in the Indian population using protaper rotary files in addition to hand instruments by evaluating the factors that might affect pain experience. Their study included One thousand three hundred and twenty-eight patients. post-operative pain was evaluated using visual analogue scale by each patient by well-defined categories at three-time intervals, 12, 24, and 48 hours. They concluded that the prevalence of post operative pain was low (4%) and the important prognostic determinants of post-operative pain were presence of pre-operative pain, old age, gender (females recorded higher), and mandibular teeth but the vitality of the tooth had no effect on the intensity nor the frequency of post operative pain.

Sadaf and Ahmad, ⁽¹⁴⁾ assessed postoperative pain and its associated clinical factors in endodontic therapy through a cross sectional study including one hundred and forty patients with premolars and molars requiring endodontic treatment and the treatment was performed in multiple visits. Results showed a significant difference in postoperative pain which was higher in females than males, mandibular teeth than maxillary teeth and in symptomatic than asymptomatic patients. There was no significant difference regarding tooth type, obturation length and sealer extrusion. So, gender, preoperative pain, maxillary, or mandibular teeth were considered risk factors affecting postoperative pain.

Mathew ⁽¹⁵⁾ reviewed and critically analyzed the influence of various factors on the incidence of postoperative pain.pain was evaluated through visual analogue scale (VAS) and facial gramice scale . A total of thirty-eight articles were included in the review, the articles were classified into variables affecting postoperative pain after endodontic treatment. Results showed high incidence of

postoperative pain in females, mandibular teeth, premolars when compared to anteriors, with positive correlation between preoperative and postoperative endodontic pain. Administration of premedication's (NSAIDs) decreases post operative pain. Step down instrumentation causes less debris extrusion and less pain. According to 13 different studies There was no significant difference between single or multiple visits. The effect of tooth vitality remained inconclusive.

Al-Rahabi ⁽¹⁶⁾ reviewed the effects of root canal treatment on postoperative pain and determined the possible predictive and related factors. Sixty-five studies were included in the review. Results showed a strong relationship existed between preoperative pain and postoperative pain, as well as high pain prevalence among women, mandibular and molar teeth. Application of intracanal medications may reduce the pain between visits. Moreover, recent advances in endodontics regarding magnification, instrumentation technique and alloy metallurgy in addition to activation of irrigant to reduce microbial load and disinfection for higher success rates of endodontic treatment reduced postoperative pain in terms of both intensity and duration. On the other hand, age of the patient and single or multiple visit root canal treatment showed no statistically significant differences.

Graunaite et al., ⁽¹⁷⁾ conducted a Split-mouth Randomized Controlled Trial to compare the effect of Resin-based and Bioceramic Root Canal Sealers on Postoperative Pain in sixty one patients with asymptomatic acute apical periodontitis (AAP) having at least 2 single rooted teeth requiring retreatment .Visual analogue scale was used to evaluate the pain .Obturation material was different for each tooth after retreatment ,they concluded that AH Plus and Total Fill perform similarly in terms of the occurrence and intensity of postoperative pain in teeth with AAP (acute apical periodontitis) with no material extrusion beyond the apex.

Nabi et al., ⁽¹⁸⁾ conducted a randomized controlled trial to compare the effect of different types of sealers on postoperative pain in single visit endodontic treatment. Ninety patients requiring primary endodontic treatment were selected for the study. Patients were treated in single visit endodontically using three different bio ceramic-based sealers (MTA plus sealer, iroot SP, Endo sequence BC) dividing the sample size to three groups. Heft–Parker Pain Rating

Scale was used to evaluate the pain for 48 hours postoperatively. They found that Post endodontic pain was reduced in all treatment groups and that the three bio ceramic sealers can be used for single-visit endodontics without fear of postoperative pain.

Fonseca et al., ⁽¹⁹⁾ Assessed extrusion and Postoperative Pain of a Bio ceramic and Resin-Based Root Canal Sealer on sixty-four patients requiring endodontic treatment in single rooted necrotic maxillary teeth, treatment was performed in a single visit and visual analogue scale (VAS) was used for pain assessment up to 1 week interval. Sealer extrusion was observed in 9 patients of the resin group and 19 patients of the bioceramic group concluding that Bio ceramic sealer presented significantly more extrusion than the Resin sealer and that sealer extrusion was not associated with pain. both groups had similar average pain level and the mean number of tablets taken for relief of pain.

Ferriera et al., ⁽²⁰⁾ compared the occurrence and intensity of postoperative pain and analgesic intake after root canal treatment, using different root canal sealers on sixty single rooted necrotic asymptomatic teeth with apical periodontitis dividing the sample to three groups according to the type of sealer used for obturation(AH Plus, Endofill or MTA Fillapex). Endodontic treatment was performed in two visits with placing calcium hydroxide dressing as intra canal medicament inter appointment . In terms of either incidence or intensity of postoperative pain or need for analgesic intake no significant differences were detected among the groups, at any timepoint. No pain was reported after 7 days. AH Plus, Endofill and MTA Fillapex used for filling root canals resulted in the same rate of postoperative pain and need for analgesic medication.

Shim et al., ⁽²¹⁾ compared the effects of bio ceramic sealer and resin-based sealer on the incidence and intensity of postoperative pain on one hundred and eight patients with anteriors and premolars and molars requiring endodontic treatment. In groups En1(premolars or anteriors) and En2(molars), root canals were obturated with Endo seal MTA using the single-cone technique. In groups AH (premolars or anteriors) and AH2(molars), the sealer used was AH Plus with the continuous wave technique. Pain was assessed through visual analogue scale over 7 days period. They found that: Endo seal MTA and AH Plus had similar

effects on the incidence and intensity of postoperative pain. The obturation time was shorter when using Endo seal MTA compared to AH Plus.

PICO

P: patients diagnosed with irreversible pulpitis age from 18-50 years old

I: obturation with bioceramic sealer

C: obturation with resin sealer

O: effect on post operative pain

Aim of the study

The aim of this randomized clinical trial is to evaluate the post-operative pain after obturation using Resin Vs. Bioceramic sealers.

Participants and Methods

I-Materials

| |
|--------------------------------------|
| Round bur/endo Z/tapered round stone |
| Rubber dam |
| #10_k files |
| Apex locator |
| #15 #20_k files |
| Side vented needle |
| 5.25% sodium hypochlorite |
| Rotary files |
| Endo motor |
| Sensor |
| Paper points |
| Gutta percha points |
| Resin sealer |
| Bioceramic sealer |
| Torch |
| Condenser |
| Cotton and temporary filling |

II-participants

A-Sample size determination:

Sample size calculation was performed using G power (3.1.9.4) software, based on a previous study ⁽²²⁾ using an alpha (α) level of 0.05 and beta (β) level of 0.85. The predicted sample size (n) is a total of 40.

B-Patient's selection:

1-Eligibility criteria:

Inclusion criteria:

- Patients age ranges from 18-50 years old.
- Patients with teeth diagnosed with symptomatic irreversible pulpitis.
- Normal periapical condition confirmed by normal periapical radiograph or that with minimal widening of the PDL space
 - The teeth are restorable
 - Teeth are periodontally free.

Exclusion criteria:

- Teeth with immature roots
- Non restorable teeth
- Medically compromised patients with systemic complication that would alter the treatment.
 - Necrotic teeth
 - Teeth with apical periodontitis or periapical lesions
 - Teeth that need multiple visits treatment

2-Ethical consideration:

Patient will be asked to follow general instructions and to sign a printed informed consent explaining the aim of study, brief of study methodology, benefits and complications of the procedure and requesting that they allow clinician to follow up after performing the treatment. This study will be performed in compliance with the ethical standards laid down in the 2013 Declaration of Helsinki

Adverse events during the trial will be reported to supervisor and co supervisor and monitors of ethical committee

C-Patient allocation:

Using computer generated randomization, the participants will be allocated randomly into two equal groups.

The sequentially numbers that will be generated, will be placed in opaque envelope until the intervention and each participant will be asked to select an envelope that determine which group of intervention he will be assigned.

D-Patient Classification:

Patients were randomly divided into two groups according to material used for obturation . each patients name will be replaced with a case number within the group to protect the privacy of medical information and data of the patients

Group (1) resin sealers

Group (2) bio ceramic sealer

Methods

Procedural steps:

- Pain scale chart will be given to each patient to rate his /her pain level before endodontic treatment as preoperative reading on a visual analogue scale (VAS)
 - Tooth will be anaesthetized using Local anesthesia containing Articaine with epinephrine 1:100,000.
 - Access cavity will be performed using a carbide round steel bur and tapered diamond stone until complete deroofing.
 - Rubber dam isolation of tooth
 - Patency is gained and working length is recorded using apex locator and confirmatory radiograph.
 - Cleaning and shaping using rotary system
 - Irrigation using 5.25% sodium hypochlorite introduced using side vented needle
 - Activation of the irrigant
 - Master cone check
 - obturation
 - temporary restoration will be placed

Methods of evaluation

Post operative pain

Each patient will be asked to fill the visual analogue scale (figure 1) to rate the pain level postoperatively at 6, 24, 48, and 72 hours following the end of the procedure.

[figure not shown]

Figure 1: Visual analogue scale used by the patient to report pain level at different time intervals

G-Statistical analysis:

Data obtained will be tabulated in the form of groups and case numbers to protect patient's confidentiality.

Data will be statistically analyzed using non-parametric tests to compare numerical variables (age, VAS scores) amongst the groups. other test will be used to evaluate the changes in pain scores over time. Categorical variables (gender, type of teeth) will be compared amongst the groups . Also, the correlation assessments between age factor and postoperative pain, and gender factor and postoperative pain will be done.

References

4. Seymour, R.A. The use of pain scales in assessing the efficacy of analgesics in post-operative dental pain. *Eur. J. Clin. Pharm.* 1982, 23, 441–444
6. Savannah, G. Bioceramic technology—The game changer in endodontics. *J Endod. Pract.* 2009, 13, 13–17.

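### Jaw, a pain predictor in all four predictor sources the protocol describes, is left to chance in a 40-patient allocation; stratifying by it is a cheap gain in precision

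*Protocol*

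**What the plan says.** - **Eligibility** (Protocol, B-Patient's selection). The criteria cover age, pulpal diagnosis, periapical and periodontal state, restorability, root maturity, general health and single-visit treatment. None limits jaw or tooth type.
- **Allocation** (Protocol, C-Patient allocation). "Using computer generated randomization, the participants will be allocated randomly into two equal groups". The generated numbers go into opaque envelopes and each patient picks one. No stratum, block or minimisation factor is named.
- **Predictors of pain** (Protocol, Review of Literature). Four sources are described. The prevalence study of 1,328 patients lists mandibular teeth among the determinants of pain. On the cross-sectional study of 140 patients the review concludes: "So, gender, preoperative pain, maxillary, or mandibular teeth were considered risk factors affecting postoperative pain". The review of 38 articles reports a high incidence in mandibular teeth. The review of 65 studies reports a strong link with preoperative pain, "as well as high pain prevalence among women, mandibular and molar teeth".
- **Analysis** (Protocol, G-Statistical analysis). "Categorical variables (gender, type of teeth) will be compared amongst the groups". Pain is related to age and gender only. Jaw is not named.
- **Size** (Protocol, A-Sample size determination). "The predicted sample size (n) is a total of 40".

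**The concern.** The protocol's own review identifies jaw as a predictor of the outcome, and jaw is known before allocation. The design nevertheless leaves its balance to chance and the described analysis does not use it. Comparing tooth type between the groups afterwards can at best reveal an imbalance; it does not correct one. It may not even show a jaw imbalance: the cross-sectional study treats jaw and tooth type as separate factors and found a difference for jaw but none for tooth type.

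At stake are precision and the readability of the result. In a trial of 40, a visible jaw imbalance would leave readers unsure how much of a VAS difference belongs to the sealer, and unexplained jaw variation costs some power.

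**Working it through.** **Inputs from the protocol:** 40 patients, two equal groups (20 and 20), alpha 0.05, no stratum. **Assumptions:** one tooth per patient; 12 to 28 of the 40 teeth mandibular (30% to 70%); a jaw effect of 0.5 to 2 cm on the 10-cm scale, or 0.5 to 1.0 within-jaw SD; power of 85%. The protocol gives neither the jaw mix nor the size of the jaw effect.

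**1. The planned sample size.** The calculation is described as "based on a previous study", "using an alpha (α) level of 0.05 and beta (β) level of 0.85". No effect size, SD or test is given, so 40 cannot be reproduced. Reading the printed beta as power of 0.85 (an assumption), 20 per group corresponds to a detectable two-sided standardised difference of 0.97 (t-test), 0.95 (normal formula: (1.960 + 1.036) × √(2/20)) or 1.00 (Mann-Whitney, efficiency 0.955). The t-test value is used in step 4.

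**2. Chance of a jaw gap.** With M mandibular teeth among 40 and a fixed 20/20 split, the number k in one arm is hypergeometric: P(k) = C(M,k) × C(40−M, 20−k) / C(40,20). The gap between arms is |2k − M| teeth.

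For M = 20: P(k = 10) = 0.2476 and P(k = 9 or 11) = 0.4093. So P(gap ≥ 4) = 1 − 0.2476 − 0.4093 = 0.343. Taking off P(k = 8 or 12) = 0.2302 gives P(gap ≥ 6) = 0.113.

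| Mandibular teeth of 40 | P(gap ≥ 4 teeth, 20 points) | P(gap ≥ 6 teeth, 30 points) | SD of gap |
|---|---|---|---|
| 12 or 28 | 0.301 | 0.082 | 14.7 points |
| 16 or 24 | 0.333 | 0.105 | 15.7 points |
| 20 | 0.343 | 0.113 | 16.0 points |

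The assumed jaw mix matters little.

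**3. Shift in the VAS difference.** Shift = gap in proportion × jaw effect. A typical gap (one SD, 0.16) gives 0.16 cm per 1 cm of jaw effect: 0.16 × 0.5 = 0.08 cm and 0.16 × 2 = 0.32 cm at the ends of the assumed range.

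**4. Power.** Take a sealer effect of 0.97 within-jaw SD, which gives 85% power once jaw is accounted for. With an even jaw mix and jaw effect e (in SD), ignoring jaw inflates the SD to √(1 + e²/4):
- e = 0.5: SD 1.031, power 83%
- e = 0.8: SD 1.077, power 79%
- e = 1.0: SD 1.118, power 76%

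**5. After stratification.** Permuted blocks of at most four within each jaw leave a gap of at most 2 mandibular teeth (about 10 points), and N stays at 40.

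**The case against.** The strongest reply is that nothing here is wrong. Simple 1:1 randomisation is valid, chance imbalance causes no bias on average, and the nominal alpha already covers it. That stands. A reader might infer from the protocol's silence on jaw that the sealer comparison is biased or its type I error inflated. It is neither. If a 30-point gap happens to occur, the false-positive chance given that gap is about 7% to 13% for jaw effects of 0.5 to 1.0 SD, but over all allocations it remains 5%.

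The size of the jaw effect is also unknown. The one cited figure that bears on it points low: the 1,328-patient study reports a pain prevalence of 4%. With an even jaw split, even if all painful teeth were mandibular and scored 10 cm, the mean jaw difference would be 0.08 × 10 = 0.8 cm. That population is not restricted to symptomatic irreversible pulpitis, so this is no ceiling here, but it is why the assumed range starts at 0.5 cm and why a typical gap, not a 13:7 split (an 11% event at most), is the fair yardstick.

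Two further inferences are tempting and unsupported. One is that the cited sealer trials show resin and bioceramic sealers to be alike, so that any true effect must be small. One of those trials compared three bioceramic sealers and had no resin arm, and the planned N rests on another study whose figures are not given. The other is that the cited trial which grouped molars apart from other teeth supports stratifying by jaw. That grouping concerns tooth type.

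It is also fair to say that all four sources name preoperative pain and sex as well. Stratifying by all three would give eight strata, on average 40/8 = 5 patients each, which is too thin. But preoperative VAS is collected and gender enters the analysis, while jaw does neither by name. The undefined tooth-type variable may include jaw, and a statistical analysis plan not shown may adjust for it. A later plan cannot, however, add strata to envelopes already prepared.

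**Conclusion.** The point holds as a worthwhile, low-cost improvement and not as an error of validity. The protocol identifies jaw as a predictor, admits both jaws, and uses jaw in neither the allocation nor the described analysis. With 20 per arm there is a 30% to 34% chance of a gap of 20 points or more, and 8% to 11% of 30 points or more, if 12 to 28 of 40 teeth are mandibular. The typical consequence is modest: about 0.08 to 0.3 cm on the VAS difference, and a loss of about 2 to 9 percentage points of power (85% to 83%, or to 76%). The probabilities depend on the assumed jaw mix only slightly. The shift and the power loss depend directly on the assumed jaw effect, for which the protocol gives no figure, and the power figures also on reading "beta (β) level of 0.85" as 85% power.

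**What to change.** 1. Record jaw (maxillary or mandibular) as a baseline field at enrolment. Eligibility can stay as broad as it is.
2. Generate one permuted-block list per jaw, with block sizes not disclosed to the operator.
3. Keep a separate set of sequentially numbered opaque envelopes for each jaw and open them strictly in order. This must replace the rule that the patient chooses an envelope: blocks balance only when their order is kept, and each jaw's set has to hold more envelopes than will be used, so free picking would not secure balance within jaw.
4. Compare VAS scores between groups with a van Elteren test (the rank-sum test stratified by jaw), which keeps the planned non-parametric approach.

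The cost is two envelope sets in place of one, one extra baseline field, and arms that may differ by a patient or two through incomplete blocks, for example 21 and 19. With blocks of four, 22 and 18 is the extreme, when both lists stop halfway through a block. The change has to be made before the envelopes are prepared.

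### The participant picks the envelope that sets the sealer group and then self-rates the pain outcome, with no shown rule withholding the sealer and no numbered order of assignment

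*Protocol*

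**What the plan says.** All references are to the Protocol.

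- **Section C (Patient allocation)** provides for computer-generated randomisation into two equal groups. On concealment it says: "The sequentially numbers that will be generated, will be placed in opaque envelope until the intervention". On assignment it says: "each participant will be asked to select an envelope that determine which group of intervention he will be assigned".
- **Section D (Patient Classification)** defines the groups by sealer: "Patients were randomly divided into two groups according to material used for obturation". It adds, as a privacy measure, that "each patients name will be replaced with a case number within the group".
- **PICO** names the intervention as "I: obturation with bioceramic sealer", with resin sealer as the comparator.
- **Procedural steps** open with the baseline score: "Pain scale chart will be given to each patient to rate his /her pain level before endodontic treatment". They continue through anaesthesia, access, isolation, working length, shaping, irrigation and its activation, and the master cone check, to obturation and the temporary restoration. Neither the draw nor the opening of the envelope is listed.
- **Methods of evaluation** has each patient complete the VAS at 6, 24, 48 and 72 hours. This is the only outcome named.
- **Section G (Statistical analysis)** has the data tabulated by group and case number, for confidentiality.
- **The introduction** gives reduced pain after obturation as the reason bioceramic sealers were put on the market.

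**The concern.** Three features of the allocation procedure bear on a self-rated outcome.

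First, the person whose choice of envelope decides the sealer is also the person who scores pain. If that person learns the sealer, the score can be coloured by what he or she expects of it. The protocol itself records the belief that one of the two products hurts less, so any such expectation would have a direction. A difference in VAS could then not be cleanly put down to the material.

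Second, generating a sequence and then letting participants choose envelopes leaves the sequence without a role in the order of assignment. The usual protection, that the next patient must receive the next number, is given up for no stated gain.

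Third, the moment at which the sealer becomes known is stated only in general terms. It should be fixed among the procedural steps, where the operator will look for it.

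**Working it through.** No figure of the plan is at issue, so the check sets the passages side by side.

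**Is the draw still random and balanced?** Inputs: a total of 40 (section A, Sample size determination) and two equal groups (section C), hence 40 / 2 = 20 per group. Assume 40 envelopes, 20 per sealer, that look identical and are drawn without replacement; the protocol does not state this. If choice is unrelated to content, each participant's chance of either sealer is 20/40 = 1/2, and the split is 20 and 20 once all are used. Under that assumption the draw introduces no bias between groups.

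**Does the generated sequence set the order?** Section C has the sequence generated and its numbers put in envelopes, then lets the participant choose among them. The k-th participant therefore receives whichever envelope is picked, not the k-th entry on the list. The number inside still allows a link back to the list if someone records it. Section C mentions no sealing, outside number or log. The only identifier described is the case number of section D, which is given within the group. It depends on assignment and does not by itself show the order of enrolment. Section G tabulates by the same identifier.

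**When does the sealer become known?** Section C holds the numbers in the envelope up to the intervention. PICO labels the intervention as obturation with a given sealer, and section D divides patients by obturation material. Read together, these put the opening at obturation, and on that reading canal preparation is finished before anyone knows the sealer. However, none of the 11 procedural steps contains the draw or the opening, so the reading is never confirmed.

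**Is the sealer kept from the rater?**

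| Place | What it adds |
|---|---|
| Section C | The participant selects the envelope; who opens it is not said |
| Ethical consideration | Consent explains the aim and briefly the methodology; nothing about withholding the group |
| Section D | Names are replaced by case numbers, for privacy |
| Methods of evaluation | The participant rates pain; no masking mentioned |
| Section G | Case numbers again, for confidentiality |

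None of these keeps the sealer from the participant through 72 hours.

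**Can a size be given?** The documents state no SD for the VAS, no effect size, and nothing on how far knowing the sealer might move a score. No size of bias follows.

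**The case against.** The strongest reply is that little here is actually wrong. The draw is by chance, the envelopes are opaque, and the timing phrase, read with PICO and section D, already points to obturation. Sealing, numbering and logging are operational details that a short protocol may leave out. The tabulation sentence is about confidentiality and does not exclude a separate allocation record. The title and consent pages and an opening passage were not available to us, so a masking statement may exist there. Section C says neither that the participant opens the envelope nor that it names a sealer.

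Most of this stands, and it rules out several stronger readings:

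- *That participant choice makes the allocation non-random.* It does not, if the envelopes are indistinguishable.
- *That assignment cannot be checked against the list.* The number is in the envelope, so a link is possible; the protocol simply describes no record of it.
- *That the participant is unmasked.* The text leaves this open and does not state it.
- *That the operator prepares canals knowing the sealer.* The introduction does list, among its factors, "Including determination of working length, degree of foraminal enlargement" and "technique of filing and instrumentation system, kinematics, trauma of periapical tissue or bacterial extrusion and root canal sealer". But it does not say that knowing the sealer changes how a canal is prepared, and the natural reading places the opening after preparation.

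The reply does not dispose of the masking gap. Allocation and masking belong in the protocol, so an unseen analysis plan does not cover them. Nor does it give a reason for letting the rater choose the envelope when a numbered sequence has already been generated.

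**Conclusion.** This is a cheap improvement, not a flaw that invalidates the trial. The stated procedure lets the participant pick the envelope and then relies on that participant's own pain score, with no shown rule withholding the sealer. It also leaves the generated list without control of the order of assignment, and leaves the time of opening to inference. No size of bias can be derived, and none is claimed.

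The conclusion rests on the text available to us and on the envelopes being indistinguishable. If they are not, the concession that the draw is random and balanced would need to be revisited. If a page we have not seen already provides for masking the participant, that part reduces to repeating the statement in section C; the points on order of assignment and time of opening remain.

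**What to change.** Amend section C and the procedural steps as follows.

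1. Use sequentially numbered, sealed, opaque envelopes, taken in number order as patients are enrolled and not chosen by the participant.
2. Add a procedural step: the envelope is opened after the master cone check and immediately before obturation. Say who opens it.
3. State that the participant is not told which sealer was used until the 72-hour VAS has been returned. If this is already stated elsewhere, repeat it in section C.
4. Give each patient an enrolment number that does not depend on group, and log it with the envelope number. The within-group case number can stay for privacy.

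The cost is a few sentences of protocol text, the numbering and sealing of envelopes already planned, and one log line per patient. The practical drawback is that an envelope has to be opened in the middle of the procedure. The treatments, the sample size and the VAS schedule do not change.

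### Case numbers run within the treatment group and the protocol prints the key, so the stated identifier reveals the sealer to anyone handling data under these codes

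*Protocol*

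**What the plan says.** Section D (Patient Classification) sets the coding rule: "each patients name will be replaced with a case number within the group to protect the privacy" of patient data. Directly below, it defines the groups: "Group (1) resin sealers" and "Group (2) bio ceramic sealer".

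Section G (Statistical analysis) carries the scheme into the data set: "Data obtained will be tabulated in the form of groups and case numbers to protect patient's confidentiality".

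The outcome is pain on the VAS, which the Review of Literature describes as "recorded through a single handwritten mark placed at one point along the length of a 10-cm line". The patient makes the mark: "Each patient will be asked to fill the visual analogue scale (figure 1) to rate the pain level postoperatively". Four such readings are planned, the first at 6 hours and the others at 24, 48 and 72 hours. A preoperative reading is taken as well (Procedural steps).

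On allocation, section C says that "each participant will be asked to select an envelope that determine which group of intervention he will be assigned". The protocol does not mention blinding of the patient, the operator, the person who reads the VAS marks or the analyst.

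**The concern.** The case number is the only patient identifier that the protocol states, and it is built on the treatment group. Both coding sentences give privacy or confidentiality as their purpose. The rule serves that purpose, but it also passes the allocation to whoever works with the codes.

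Two later steps could be affected. Someone has to turn each handwritten mark into a number, which leaves room for rounding and for decisions on unclear or blank marks. Someone then has to analyse the scores, and section G names the tests only in general terms. The introduction says that bioceramic sealers were marketed as causing less pain, so a person who knows the sealer may have a direction in mind. The operator has to know which sealer is used. Reading and analysis do not require that knowledge, and they can be masked at almost no cost.

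**Working it through.** The point concerns coding and has no planned figure to reproduce. The sample size of 40 plays no part in it beyond the counts below.

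**Does the identifier carry the arm?**
1. Section D: the number runs within the group. Case 7, for example, can then exist in both groups, so the number is unique only as the pair (group, number).
2. Section D: group 1 is resin and group 2 is bioceramic. The key to the first half of the pair is printed in the protocol.
3. Section G: the data are laid out by that same pair.
4. It follows that a person who holds a record under these codes, and the protocol, knows the sealer for that record.

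**How many readings are filed under such a code?**
- All readings: 40 patients × 5 times (preoperative, 6, 24, 48, 72 h) = 200.
- Postoperative readings, which bear on the comparison of sealers: 40 × 4 = 160.
- The other 40 are preoperative. They are marked before treatment, while section C keeps the allocation in the envelope until treatment. A within-group number may therefore not exist when that chart is filled in, although it may be attached later.

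**How large could an effect on the readings be?** The documents give no reading error, so only an assumption is possible. If knowledge of the arm moved the readings of one group against the other by d, the difference in location between the groups would move by d, and more patients would not average it away. With d assumed to be 0.1 to 0.3 cm, this is 0.1/10 = 1% to 0.3/10 = 3% of the 10-cm line. If the same d also applied to the preoperative reading, it would cancel in changes from baseline. The range only illustrates scale. Nothing in the protocol shows that d differs from zero.

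**What the text leaves open.** It does not say who measures the marks, whether the charts carry the case number or the group, or who holds the allocation list.

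**The case against.** The strongest reply is that these are privacy sentences, which do not forbid masking. Much of that reply stands.

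- A reader might infer that whoever measures the VAS marks sees the sealer. The text does not show this, because it names no measurer and does not say what the charts carry. The inference is natural, since no other identifier is stated, but it remains an inference.
- A reader might infer that no blind of data handling can hold. That is too strong. Any between-group test needs a group column, and a table with neutral labels and the key withheld would still fit section G.
- A reader might infer that the coding breaks a promised blind. The protocol promises none, so nothing is contradicted. Masking of the analyst, data lock and release of the key are also commonly left to a statistical analysis plan, which is not at hand, and their absence is not the point here.
- The score is the patient's own mark, so a reader's knowledge can affect only how an existing mark is measured or handled.
- The expectation in favour of bioceramic sealers is tempered by the protocol itself. It states a null hypothesis of no difference, and the bioceramic-versus-resin trials it summarises report similar pain.

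What the reply does not remove is the stated numbering rule. The protocol fixes it in two places, it discloses the allocation, and it gives no privacy that a trial-wide number would not give.

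**Conclusion.** The point holds in a limited form. The numbering rule and the printed key together reveal the sealer to anyone who handles data under these codes, and the protocol describes no masking of reading or analysis to offset this. That much follows from the text alone.

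Any effect on the results is only a possible bias. Its size is unknown and probably small. It would require the code to be visible when the marks are read or the analyses chosen, and that knowledge to influence how this is done. The documents establish neither condition. The point is of low severity and worth acting on because the change costs almost nothing.

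**What to change.** In section D, replace the within-group case number by one trial-wide number, 1 to 40 in order of enrolment, that does not depend on the arm. Put only this number on the VAS charts, and keep the link between number and sealer on a separate list. A number given at enrolment is also available for the preoperative chart.

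In section G, state that the data are tabulated and analysed with neutral group labels A and B, and that the key is opened only after all marks are measured, the data are locked and the tests are run.

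The cost is two sentences in the protocol and one separate list, with no extra staff, visits or patients. The small downside is that the key has to be kept apart until then.
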